Symptoms of Hedgehog Inhibitor Toxicity: At each visit subjects will be asked if they have experienced any symptoms that have been associated with systemic use of this class of drugs, in particular hair loss, taste loss, muscle cramps, bowel changes, fatigue.

Adverse Events: During the study, subjects will be assessed for the occurrence of new and ongoing AEs. Descriptions of AEs will include the dates of onset and resolution (if resolved), maximum severity, and seriousness, action taken regarding the study drug, corrective treatment, outcome, and the Investigator's assessment of causality. AEs present at any visit will be followed to resolution (return to normal or to the baseline state) or until clinically stable as determined by the Investigator.

Safety Laboratory Tests: Routine safety laboratory tests (complete blood count/differential urinalysis and serum chemistry) will be performed at Screening, Week 6, and Week 12. Any out-of-range laboratory result that is considered clinically significant by the Investigator will be recorded as an AE and should be confirmed by repeat testing at the discretion of the Investigator. Clinically significant laboratory abnormalities at any visit will be followed to resolution (return to normal or to the baseline state) or until clinically stable as determined by the Investigator.

Physical Examinations: An abbreviated physical examination including measurements of height, weight, and vital signs (blood pressure, heart rate, respiration rate, and oral temperature) will be performed at Baseline and Week 12.

Pregnancy Tests: All female subjects will have a pregnancy test performed at the Screening visit. Females of childbearing potential will take a home pregnancy urine test at Weeks 2, 8, and 10 and will have a serum pregnancy test at Weeks 6 and 12.

Efficacy Measurements:

Primary:

Biomarker: At screening the treatment-targeted BCC will be biopsied to confirm the clinical diagnosis of nodular BCC. In addition, at or within 14 days of the Week 12 visit the

treatment site will be excised. Both of these tissue samples will be tested for GLI1 mRNA levels.

Secondary:

The clinical efficacy of patidegib as defined by the percent decrease from Baseline of the longest diameter of treatment-targeted BCC after 12 weeks of treatment.

Exploratory:

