The exploratory analysis of ISGTA will be analyzed with a Cochran-Mantel-Haenszel test

Safety:

Safety Endpoints:

- Adverse Events
- Dermal Safety and Tolerability including pain/burning, pruritus, erythema, edema, and scabbing/crusting
- Clinical laboratory assessments

Safety Analyses:

Subjects will be assessed for the occurrence of new and ongoing AEs. Descriptions of AEs will include the dates of onset and resolution (if resolved), maximum severity, seriousness, action taken regarding the study drug, corrective treatment, outcome, and Investigator's assessment of causality. All AEs will be recorded and classified using terminology from the Medical Dictionary for Regulatory Activities (MedDRA). All reported treatment-emergent AEs (TEAEs), defined as any AE with an onset on or after the date of first study drug application, will be summarized by treatment group, the number of subjects reporting TEAEs, system organ class, preferred term, severity, and relationship to study drug. When summarizing TEAEs by severity or relationship to study drug, each subject will be counted only once within a system organ class or a preferred term using the event with the greatest severity or causality, respectively, within each category. All reported serious adverse events

(SAEs) will be summarized by treatment group, the number of subjects reporting SAEs, system organ class, preferred term, severity, and relationship to study drug.

All information pertaining to AEs noted during the study will be listed by subject and will include a verbatim description of the event as reported by the Investigator, as well as the preferred term, system organ class, start date, stop date (if stopped), seriousness, severity, action taken regarding the study drug, corrective treatment, outcome and relationship to the study drug. In addition, a listing of subjects who prematurely discontinue from the study due to AEs will be provided as well as a listing of subjects who reported an SAE.

The frequency of dermal safety and tolerability assessments including pain/burning, pruritus, erythema, edema, and scabbing/crusting will be summarized by treatment group and visit.

Changes from baseline in safety laboratory values and vital sign measurements will be summarized with descriptive statistics for each treatment group at all applicable study visits.

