Subjects will return their tubes of study drug, which will be evaluated for drug usage compliance. While individual usage rates of topical products will vary, the use of a dosing card should help limit the variation in dosing inherent with topical products. Approximately 20 mg of the gel represents a single applied dose. Thus a subject treating a single tumor once daily for 12 weeks will apply a total dose of 1.6 gm of gel and those treating two tumors twice daily for 12 weeks will apply a total dose of 6.4 gm of gel. In terms of actual drug, 20 mg of patidegib gel 2% and 4% contains 0.4 mg and 0.8 mg of patidegib, respectively. Thus the total dose of drug in the 2% once daily group treating a single tumor will be approximately 34 mg while subjects treating two tumors twice daily for 12 weeks with patidegib gel 4% will receive a total of 134 mg of patidegib. To put this in perspective in previous trials with an oral formulation of patidegib subjects were treated with a daily oral dose of 130 – 160 mg, many for longer than 6 months.

Upon completion of the 12-week treatment period, all subjects will be asked to return to the investigational center for final evaluation. At the Week 12 visit the treatment site(s) will be excised. The area excised should at a minimum include the original diameter of the tumor. This means that if the tumor has shrunk in size the entire original area of the BCC will be excised, not just the visually apparent residual tumor. During the study, subjects will be allowed to use moisturizers and emollients and sunscreen. The Investigator will assess the areas affected at each visit.

The treatment-targeted BCC(s) will be identified by the Investigator at the Baseline visit and will be circled in ink at Baseline, Weeks 6 and 12, and photographed, and measured at all study visits (Baseline, Weeks 2, 6, 8, 10, and 12).

Biomarkers: On each subject one or two baseline previously untreated nodular BCCs designated as a treatment-targeted tumor will be biopsied and at the end of 12 weeks of treatment the treatment

PellePharm, Inc.

Dose Escalating Study in Sporadic Basal Cell Carcinomas

site(s) will be excised. Both samples will be evaluated histologically and for determination of GLI1 mRNA levels.

Blood samples for complete blood count and serum chemistry and urine for urinalysis will be collected from subjects at Screening, Week 6, and Week 12.

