9.3.5.2 Documenting Adverse Events

It is the responsibility of the Investigator to document all AEs that occur during the course of the study. The AEs should be documented as a single medical diagnosis. When this is not possible, the AE should be documented in terms of signs and/or symptoms observed by the Investigator or reported by the subject at each study visit.

All AEs occurring after the subject signs the informed consent through the last study visit must be reported, regardless of whether or not the AEs are considered drug-related. All AEs, whether in response to a query, observed by the study site personnel, or reported spontaneously by the subject, will be recorded.

At each visit during the study, the subject will be assessed for the occurrence of new and ongoing AEs. Dermal safety and tolerability that result in the subject's requiring a concomitant therapy or discontinuation from the study will be reported as an AE. The following data will be collected on all AEs and recorded on the appropriate CRF:

- Event name (diagnosis preferred, if unknown, record the signs/symptoms)
- Onset date and end date
- Maximum intensity (severity)
- Seriousness
- Action taken regarding study drug
- Corrective treatment, if given
- Outcome

In addition, the Investigator's assessment of causality will be recorded.

Vital sign abnormalities are to be recorded as AEs only if they are clinically significant (for example: are symptomatic, requiring corrective treatment, leading to discontinuation or fulfilling a seriousness criterion).

Subjects will be questioned about any concurrent illness or systemic sign or symptom including but not limited to fatigue, loss or change in taste, nausea, vomiting, alopecia, diarrhea, and muscle spasms. Any incidence of these systemic signs or symptoms will be reported on the AE eCRF.

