6.8.2 Adverse Events

All AEs that occur during the study will be recorded and classified on the basis of Medical Dictionary for Regulatory Activities (MedDRA) terminology. Treatment-emergent Aes (TEAEs) are defined as Aes with an onset on or after the date of the first study drug application. Adverse events noted prior to the first study drug administration that worsen after Baseline will also be reported as Aes and included in the summaries.

Treatment-emergent Aes will be summarized by treatment group, the number of subjects reporting a TEAE, SOC, preferred term, severity, relationship to study drug (causality), and seriousness. When summarizing Aes by severity and relationship, each subject will be counted once within a system organ class or a preferred term by using the event with the highest severity and greatest relationship within each classification.

If relationship to study drug is reported as unknown, possible, probable or definite, then this is defined as related. If relationship to study drug is reported as unlikely or not related, then this is defined as unrelated.

Serious Aes will be summarized by treatment group, severity and relationship to study drug.

Listings will be presented for all adverse events as well as for serious adverse events and adverse events leading to study drug withdrawal.

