Note: Treatment-emergent adverse events are those with an onset after use of study medication.

^a Counts reflect numbers of subjects reporting one or more adverse events that map to MedDRA dictionary (Version 19.0). At each level of summarization (System Organ Class or Preferred Term) subjects are counted once.

Table 14.3.2.1.3: Summary of Treatment-Emergent Adverse Events by Severity (Safety Population)
(Page 1 of xx)

System Organ Class ^a Preferred Term	Severity	Patidegib Gel 2% QD N=xx)	Patidegib Gel 2% BID (N=xx)	Patidegib Gel 4% QD (N=xx)	Patidegib Gel 4% BID (N=xx)	Vehicle Gel (N=xx)
System Organ Class	Mild	xx (xx.x%)	xx (xx.x%)	xx (xx.x%)	xx (xx.x%)	xx (xx.x%)
	Moderate	xx (xx.x%)	xx (xx.x%)	xx (xx.x%)	xx (xx.x%)	xx (xx.x%)
	Severe	xx (xx.x%)	xx (xx.x%)	xx (xx.x%)	xx (xx.x%)	xx (xx.x%)
Preferred Term	Mild	xx (xx.x%)	xx (xx.x%)	xx (xx.x%)	xx (xx.x%)	xx (xx.x%)
	Moderate	xx (xx.x%)	xx (xx.x%)	xx (xx.x%)	xx (xx.x%)	xx (xx.x%)
	Severe	xx (xx.x%)	xx (xx.x%)	xx (xx.x%)	xx (xx.x%)	xx (xx.x%)

Note: Treatment-emergent adverse events are those with an onset after use of study medication.

^a Counts reflect numbers of subjects reporting one or more adverse events that map to MedDRA dictionary (Version 19.0). At each level of summarization (System Organ Class or Preferred Term) subjects are counted once under the greatest reported severity.

Table 14.3.2.1.4: Summary of Treatment-Emergent Adverse Events by Relationship (Safety Population)
(Page 1 of xx)

System Organ Class ^a Preferred Term	Relationship	Patidegib Gel 2% QD (N=xx)	Patidegib Gel 2% BID (N=xx)	Patidegib Gel 4% QD (N=xx)	Patidegib Gel 4% BID (N=xx)	Vehicle Gel (N=xx)
System Organ Class	Unrelated	xx (xx.x%)	xx (xx.x%)	xx (xx.x%)	xx (xx.x%)	xx (xx.x%)
	Related	xx (xx.x%)	xx (xx.x%)	xx (xx.x%)	xx (xx.x%)	xx (xx.x%)
Preferred Term	Unrelated	xx (xx.x%)	xx (xx.x%)	xx (xx.x%)	xx (xx.x%)	xx (xx.x%)
	Related	xx (xx.x%)	xx (xx.x%)	xx (xx.x%)	xx (xx.x%)	xx (xx.x%)

Note: Treatment-emergent adverse events are those with an onset after use of study medication. Not Related includes Not Related and Unlikely, Related includes Possible, Probable, or Definite.

^a Counts reflect numbers of subjects reporting one or more adverse events that map to MedDRA dictionary (Version 19.0). At each level of summarization (System Organ Class or Preferred Term) subjects are counted once under the strongest reported relationship.

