	- (-		C: System Organ Class P: Preferred Term V: Verbatim	F: Date of First Application S: Start Date (Day) 1	S: Severity R: Relationship to Study Drug E: Serious	
Subject	Age/Sex	Eval	T: In Treatment Area	E: End Date (Day) 1	O: Outcome	A: Action Taken
xxxxxx	xxxx	xxxxxxx	S: xxxxxxxxxxxx	F: xxxxxxxxx	S: xxxx	A: xxxxxxxxxxx
^^^^	AAAA	*******	P: xxxxxxxxxxxxx	S: xxxxxxxxx xxxx	R: xxxxxxxxx	A. AAAAAAAAAAA
			V: xxxxxxxxxxxx	E: xxxxxxxxx xxxx	E: xx	
			T: xx		O: xxxxxxxx	
			S: xxxxxxxxxxxxx	F: xxxxxxxxx	S: xxxx	A: xxxxxxxxxxxx
			P: xxxxxxxxxxxxx	S: xxxxxxxxx xxxx	R: xxxxxxxxxx	
			V: xx	E: xxxxxxxxx xxxx	E: xxx	
			T: xx		O: xxxxxxxx	
xxxxxx	xxxx	xxxxxxx	S: xxxxxxxxxxxxx	F: xxxxxxxxx	S: xxxx	A: xxxxxxxxxxxx
			P: xxxxxxxxxxxxx	S: xxxxxxxxx xxxx	R: xxxxxxxxx	
			V: xxxxxxxxxxxx	E: xxxxxxxxx xxxx	E: xx	
			T: xx		O: xxxxxxxx	

SOURCE: USERNAME\SPONSOR\PROJECT\JOBNAME (DATE, TIME)

Listing sorted by Subject Number, Start Date, End Date, and Adverse Event.

Note Action Taken will consist of a concatenation of Action Taken Regarding Study Drug, Action Taken Regarding Hospitalization, Action Taken Concomitant Medication, Action Taken Procedure/Therapy, Action Taken Other, and Specify

Day is calculated as date - Date of first dose for dates prior to Baseline. Otherwise, day is calculated as
date - Date of first dose + 1 for dates on or after Baseline.
Note: System Organ Class and Preferred Term map to the MedDRA dictionary (Version 19.0).

Listing 16.2.7.2.3: Treatment-Emergent Serious Adverse Events Treatment Arm (Page xx of yy)

			C: System Organ Class P: Preferred Term	F: Date of First Application	S: Severity R: Relationship to Study Drug	
Subject	Age/Sex	Eval	V: Verbatim T: In Treatment Area	S: Start Date (Day) ¹ E: End Date (Day) ¹	E: Serious O: Outcome	A: Action Taken
xxxxx	xxxx	xxxxxxx	S: xxxxxxxxxxxx	F: xxxxxxxxx	S: xxxx	A: xxxxxxxxxxx
			P: xxxxxxxxxxxxx	S: xxxxxxxxx xxxx	R: xxxxxxxxxx	
			V: xxxxxxxxxxxxxx	E: xxxxxxxxx xxxx	E: xx	
			T: xx		O: xxxxxxxx	
			S: xxxxxxxxxxxxx	F: xxxxxxxxx	S: xxxx	A: xxxxxxxxxxxx
			P: xxxxxxxxxxxxx	S: xxxxxxxxx xxxx	R: xxxxxxxxxx	
			V: xx	E: xxxxxxxxx xxxx	E: xxx	
			T: xx		O: xxxxxxxx	
xxxxxx	xxxx	xxxxxxx	S: xxxxxxxxxxxxx	F: xxxxxxxxx	S: xxxx	A: xxxxxxxxxxxx
			P: xxxxxxxxxxxxx	S: xxxxxxxxx xxxx	R: xxxxxxxxx	
			V: xxxxxxxxxxxx	E: xxxxxxxxx xxxx	E: xx	
			T: xx		0: xxxxxxxx	

Note: System Organ Class and Preferred Term map to the MedDRA dictionary (Version xx.x).

SOURCE: USERNAME\SPONSOR\PROJECT\JOBNAME (DATE, TIME)

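### The treatment-emergent AE period has no end, so complications of the end-of-treatment excision enter the overall TEAE tables by arm and dilute the descriptive safety contrast

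*Protocol*

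**What the plan says.** The protocol Synopsis (Safety Analyses) and Section 10.8.2 give the same definition: TEAEs are "defined as any AE with an onset on or after the date of first study drug application". SAP 6.8.2 follows: they "are defined as Aes with an onset on or after the date of the first study drug application". It adds events present before dosing that worsen later. The footnotes to the TEAE shells in SAP Section 10 read "Treatment-emergent adverse events are those with an onset after use of study medication". Each version sets a start and none sets an end.

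On surgery, Protocol 5.1 states "At the Week 12 visit the treatment site(s) will be excised". On reporting, Protocol 9.3.5.2 states "All AEs occurring after the subject signs the informed consent through the last study visit must be reported". Protocol Section 9 names Week 14, whose only listed procedure is a healing check of the surgical site, among the in-person study visits.

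The adverse event listing in SAP Section 11 carries a location marker, "T: In Treatment Area".

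**The concern.** Safety and tolerability is the first primary objective, and each active regimen has only 6 subjects. Under the protocol every subject who completes treatment has surgery on the treated skin. With no end to the treatment-emergent period, wound pain, bleeding, infection or poor healing reported by the last visit is tabulated alongside events that began while gel was being applied.

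Two things are at stake. A surgical background shared by all arms makes any gel-related difference in the share of subjects with an AE look smaller. And because a subject is counted once at the greatest severity, a surgical event can displace a milder gel-phase grade. The location marker cannot help, because the wound is the treatment area.

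**Working it through.** **Which events are caught.**

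1. Start: first application, in all four places (Protocol Synopsis and 10.8.2; SAP 6.8.2 and the Section 10 footnotes). End: none stated.
2. Reporting runs to the last study visit (Protocol 9.3.5.2). Nominally this adds Day 85 to Day 99, which is 14 days. With the visit windows in Table 1 the tail runs from 92 - 88 = 4 days to 106 - 82 = 24 days.
3. No rule in either document removes or separates events that begin after the excision.

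**Which tables separate them.** Table 14.3.2.1.1 page 1 (any AE, maximum severity), Table 14.3.2.1.2 (system organ class and preferred term) and the severity table 14.3.2.1.3 pool all TEAEs. The relationship rows of Table 14.3.2.1.1, its page 2 and Table 14.3.2.1.4 split them into related and unrelated. The protocol's causality scale (9.3.5.5) rates relationship to study drug and has no separate procedure category. The AE data items in 9.3.5.2 include no procedure-relationship field.

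**Size.** The documents give no AE rates, so there is no plan figure to reproduce. Let p be the gel-phase risk of at least one AE in an arm and q the risk of an excision AE, equal in all arms and independent of the gel. The observed risk is 1 - (1-p)(1-q), and the arm difference is (p1 - p0)(1-q). Assumed for illustration: p1 = 40% on active, p0 = 15% on vehicle, q from 10% to 30%. The last two columns are 36 × q and 1 - (1-q)^6, and they take every subject as excised.

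| q | Active | Vehicle | Difference (points) | Expected subjects of 36 with an excision AE | Chance of at least one in a 6-subject arm |
|---|---|---|---|---|---|
| 0% | 40% | 15% | 25 | 0 | 0% |
| 10% | 46% | 23.5% | 22.5 | 3.6 | 47% |
| 20% | 52% | 32% | 20 | 7.2 | 74% |
| 30% | 58% | 40.5% | 17.5 | 10.8 | 88% |

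**Severity.** Within a system organ class or preferred term, SAP 6.8.2 keeps the highest grade per subject. Protocol 9.3.5.4 grades severity partly by the medical intervention needed. A treated wound complication can therefore supersede a milder gel-phase event in the same class or term, and in the overall maximum-severity rows.

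**Whether the data are collected consistently.** The passages do not agree:

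- *Excision timing.* Protocol 5.1 puts it at the Week 12 visit. Table 1 footnote h requires it within 48 hours of that visit. In the Synopsis (Efficacy Measurements), "at or within 14 days of the Week 12 visit the" site is to be excised.
- *AE collection after excision.* Section 9.3.5.2 requires reporting to the last visit, but Table 1 marks AEs through Week 12 and not at Week 14. In 9.1.4 AEs are recorded (step 2) before the excision (step 6), and the subject is then exited (step 10). Section 9.1.5 lists only the healing check, which SAP Section 11 puts in its own listing (16.2.8.5).

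Post-excision events are thus reportable under one section and unscheduled under others, so capture may be uneven.

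**The case against.** A reader might infer that surgical complications are counted as caused by the gel. The documents do not support that. Treatment-emergent is a label of timing. Protocol 9.3.5.5 lists a direct link to study procedures among the considerations for causality, although its lead-in refers to serious events. SAP 6.8.2 reports events judged unlikely or not related as unrelated, and Table 14.3.2.1.4 applies that split to every class and term. This stands. What remains is that the separation rests on opinion about a wound in skin treated for 12 weeks, and that the SAP counts an unknown relationship as related, a category the protocol scale does not contain.

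A reader might also infer a false excess in some arm, or a spoiled primary safety comparison. With q equal across arms the model gives dilution only. The analysis is descriptive (SAP 6.1). Dermal tolerability and systemic symptoms are tabulated separately by visit through Week 12, and preferred terms that surgery does not produce are unaffected. The shift is also small beside the arm size: 2.5 to 7.5 points, when one subject in 6 is 16.7 points. All of this stands and limits the point.

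Finally, with 36 subjects the AE listing gives start day, verbatim term and relationship, so a reader could pick out post-excision events by hand. That is possible, but it is not a planned summary, and events starting on the day of surgery cannot be placed because onset is recorded by date only.

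**Conclusion.** The point holds as a gap in definition with a modest effect. Excision complications reported by the last visit count as TEAEs in the subject's arm and enter the any-AE, class/term and severity tables unseparated. The dilution factor for at least one AE is (1-q). At an assumed q of 10% to 30%, an assumed 25-point difference becomes 22.5 to 17.5 points, and the chance that a given 6-subject arm contains at least one such event is 47% to 88%. Maximum-severity rows can also lose a milder gel-phase grade. These figures rest on assumed rates, on q being equal across arms and on independence from the gel. If the gel affects healing, or if the number of excised sites differs by arm, the effect would not be pure dilution. The documents do not show that these events are attributed to the gel or that one arm is systematically disadvantaged.

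**What to change.** 1. Keep the overall TEAE tables as they are, so that late gel effects are not removed. For Tables 14.3.2.1.1 to 14.3.2.2.4, also present TEAEs by onset before versus after the end-of-treatment (Week 12/ET) excision, by arm, and state the rule in SAP 6.8.2 and Protocol 10.8.2.
2. Tie the split to the end-of-treatment excision and not to the first removal of any target. Protocol 6.3 lets a subject have one of two target tumors treated and remain in the trial; a cut there would label AEs during continued gel use on the other tumor as post-excision.
3. Record the actual excision date, and a before/after mark for AEs that start that day. The tumor listing (16.2.6.1) shows only an excised mark against a visit date.
4. Reconcile the passages on excision timing (Synopsis, 5.1, Table 1 footnote h) and on AE collection after Week 12 (Table 1, 9.1.4, 9.1.5, 9.3.5.2). Without this the post-excision part would rest on uneven capture.

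The cost is one derived flag, one eCRF mark (plus the excision date if it is not already captured) and extra table columns. The post-excision counts will be small and should be read descriptively.

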3. LIST OF ABBREVIATIONS AND DEFINITIONS OF TERMS

Abbreviation or	Definition or Explanation
Specialist	
Term	
AE	Adverse Event
ALT	Alanine Aminotransferase
API	Active Pharmaceutical Ingredient
AST	Aspartate Aminotransferase
ANCOVA	Analysis of Covariance
BCC	Basal Cell Carcinoma
BCNS	Basal Cell Nevus Syndrome
BUN	Blood Urea Nitrogen
CBC/Diff	Complete Blood Count with Differential
CLL	Chronic Lymphocytic Lymphoma
eCRF	Electronic Case Report Form
ET	Early Termination
FDA	Food and Drug Administration
FSH	Follicle-Stimulating Hormone
GCP	Good Clinical Practice
GLI 1	Glioma-associated oncogene homolog 1
GMP	Good Manufacturing Practices
GRAS	Generally Recognized as Safe
HC1	Hydrogen Chloride
НН	Hedgehog
ICF	Informed Consent Form
ICH	International Conference on Harmonization
IEC	Independent Ethics Committee
IND	Investigational New Drug
IRB	Institutional Review Board
ISGTA	Investigator Static Global Tumor Assessment
ITT	Intent-to-Treat
LOCF	Last Observation Carried Forward
MedDRA	Medical Dictionary for Regulatory Affairs
MCH	Mean Corpuscular Hemoglobin
MCHC	Mean Corpuscular Hemoglobin Concentration
MCV	Mean Corpuscular Volume
mRNA	Messenger Ribonucleic Acid
PDT	Photodynamic Therapy
PTCH1	Patched Protein 1
PSCP	Primary Skin Care Physician
RBC	Red Blood Cell
SAE	Serious Adverse Event

Abbreviation or	Definition or Explanation
Specialist	
Term	
SAP	Statistical Analysis Plan
SAS	Statistical Analysis System
SEB	Surgically Eligible Basal Cell Carcinoma
SMO	Smoothened
SPF	Sunscreen Protection Factor
SAP	Statistical Analysis Plan
TEAE	Treatment-Emergent Adverse Event
US	United States
UV	Ultraviolet
WBC	White Blood Cell Count

